ACCORDS

ADULT AND CHILD CENTER FOR OUTCOMES
RESEARCH AND DELIVERY SCIENCE

UNIVERSITY OF COLORADO
CHILDREN'S HOSPITAL COLORADO

Supporting the implementation of a state policy on screening for Adverse Childhood Experiences (ACEs) in Federally Qualified Health Centers.

Study Protocol Document

NCT: 04916587

Date: 07.20.2024

COMIRB Protocol

COLORADO MULTIPLE INSTITUTIONAL REVIEW BOARD
[name] [contact] [contact]

Protocol #: 22-0547

Project Title: Supporting the implementation of a state policy on screening for Adverse Childhood Experiences (ACEs) in Federally Qualified Health Centers.

Principal Investigator: [name] [name].

Version Date: 05/10/2024

I. Background/Rationale [previously iStar section 11 (exempt) or 12 (expedited/full board)]

Background

- Adverse Childhood Experiences (ACEs) refer to traumatic events occurring before age 18, such as maltreatment, family separation and exposure to violence.
- ACEs are pervasive among children ages 0 – 17 years old in the United States with 45% experiencing at least one ACE and 10% experiencing three or more ACEs. These events place children at high risk for negative life outcomes if left undetected and untreated.
- Early screening for ACEs is a national public health priority but health care providers seldom use these screenings during routine wellness checks.
- This study leverages the Surgeon General of the state of California's 2020 ACEs screening policy (ACEs Aware), which is supported by an annual \$40.8 million budget. Starting January 2020, the state's Medicaid health care program will reimburse primary care settings for implementing ACEs screenings annually during well-child visits.

Justification

- There is evidence that increased mental health screening campaigns alone often do not translate into higher access to services for children and they may in fact exacerbate disparities by increasing stigma and reinforcing a deficit view of marginalized groups.
- One reason why these efforts do not meet expected outcomes is the fact that they lack an evidence-based implementation plan to successfully deliver the screening programs/policies in local contexts.
- This study is needed to fill that gap as, in partnership with a trauma-informed workgroup, we will develop and test implementation strategies suited for pediatric screening in community-based health centers in California.

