4.11 Months 8 – 36: The study's data analyst will lead data preparation and analysis and will meet weekly with the PI, research team and clinical partners to go over progress and troubleshoot.

4.12 Months 22-42: Preparation of the R01 proposal and sharing of results with clinical partners. Dissemination of results.

See a timeline summary table of the trial activities below:

2. The intervention will be implemented at five partner FQHC clinics. Handheld computer tablets will be provided to clinic screening staff with the REDCap web application database (implementation strategy). The tablets will enable clinic screening staff to administer the PEARLS and BPSC/PPSC assessments by the medical assistant (screener) to the caregiver of the child patient prior to the wellness visit. After these assessments have been conducted using the tablet, the screening staff will hand the tablet to the primary-care provider. The tablet will then guide the primary-care provider to complete the ACEs-related conditions checklist provided by the state. The REDCap web application algorithm will use the information from the PEARLS, PSC and ACEs-related health

conditions checklist to determine whether the child is deemed to be at low, medium, or high risk for toxic stress and/or caregiver concerns about the child's emotional/behavioral development. If the child is determined to be at high risk, the web application will prompt the primary-care provider to make a referral to mental-health and support services.

3. Steps that will be taken to protect participant privacy and confidentiality:

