Quantitative data: We will use descriptive statistics (i.e., frequencies, means and standard deviation estimates) to describe the analytical sample. We will examine whether the implementation strategies (i.e., advisory board, use of REDCap handheld tablets, use of the PSC tool and an implementation coach) increases the number of children screened and referred to support services, compared to baseline. To do that, we will use methodology that accounts for repeated measures over time and that accounts for both within-person and across-person variation (i.e., Generalized linear mixed model (GLMM)) while controlling for clustering of patients within clinics and possible confounding by calendar time. *Our analysis will include sex as a biological variable, testing for a differential effect on outcomes by child sex.* We will report the magnitude of missing data and compare demographic and clinic characteristics and outcomes between observations with versus without missing data. In sensitivity analyses, we will perform multiple calculations (i.e., imputations) using fully conditional specification to obtain 10 complete datasets; summary estimates of intervention effects with 95% confidence limits over the 10 datasets will incorporate within- and between-dataset sampling variability.

Comparison of randomized intervention sites to non-randomized control sites

Due to the human and financial impact of COVID-19 epidemic, the randomized control periods had not implemented ACEs screening at the time of the pilot starting. We have identified two clinics that have implemented ACEs screening that are not part of the trial.

To obtain an additional non-randomized estimate of the intervention effect, we will compare:

- (1) the control periods in the randomized clinics to comparable time periods in the non-randomized clinics;
- (2) the intervention periods in the randomized clinics to comparable time periods in the non-randomized clinics.

We will use the same GLMM models as described above, with indicator variables for non-randomized vs randomized clinic, and randomized control vs intervention periods. Groups will be compared on ACEs screenings, and mental health referral rates.

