ACCORDS

ADULT AND CHILD CENTER FOR OUTCOMES
RESEARCH AND DELIVERY SCIENCE

UNIVERSITY OF COLORADO
CHILDREN'S HOSPITAL COLORADO

Supporting the Implementation of a State Policy on Screening for Adverse Childhood
Experiences (ACEs) in Federally Qualified Health Centers (FQHC).

Statistical Analysis Plan

NCT: 04916587

Date: 7.20.2024

Statistical Analysis Plan

Title of Study: Supporting the Implementation of a State Policy on Screening for Adverse Childhood Experiences (ACEs) in Federally Qualified Health Centers (FQHC)

NIMH Study ID Number: R21MH123835

Clinical Trial Number: NCT04916587

Sponsor: Study funded by the National Institute of Mental Health.

Principal Investigator: [name] [name].

Summary and research objective(s):

Screenings for Adverse Childhood Experiences (ACEs) promote early identification of toxic stress and potential trauma, allowing for intervention and possible amelioration of detrimental effects of the ACEs. The state of California enacted a 2020 fee-for-service healthcare policy, ACEs Aware, reimbursing clinics for annual ACEs screenings during well-child visits, but did not provide guidance on screening implementation. This study aims to test the effectiveness and acceptability of a multifaceted implementation strategy for implementing ACEs screenings, in partnership with a Federally Qualified Health Center (FQHC) system in California that adopted the ACEs Aware policy in August of 2020.

The proposed strategy is comprised of personnel training (e.g., Trauma-informed care), integrated technology with a customized screening scoring and aligned service referral algorithm, team-based screening workflows, ongoing care team coaching, and peer support. Significant changes to the original study protocol were needed to accommodate the negative impact that the COVID-19 pandemic had in the partner FQHC system.

Hypotheses

1. ACEs screenings

- a. Clinics using implementation strategies will have higher rates of REACH of ACEs screenings compared to their screening rates before implementing the strategies.
- b. Clinics using implementation strategies will have higher rates of REACH of ACEs screenings than clinics screening for ACEs and as part of the state funded CALQIC project, without the implementation strategies.

- c. Exploratory: Are there any differences between in the effectiveness of the implementation strategies in different sub-groups (such as race, ethnicity, age and gender)?

2. Referrals to mental health services

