- a. Clinics using implementation strategies will have higher rates of mental health referrals compared to their referral rates before implementing the strategies.
- b. Clinics using implementation strategies will have higher rates of mental health referrals than clinics screening for ACEs and as part of the state funded CALQIC project, without the implementation strategies.
- c. Among children screened, ACEs screenings indicating medium and high risk will lead to mental health referrals at higher rates than screenings indicating low risk.
- d. Exploratory: Are there any differences between in the effect of the implementation strategies on referrals in different sub-groups (such as race, ethnicity, age and gender)?

[figure not shown]
3. Implementation outcomes

- a. Perceive feasibility, acceptability, and usefulness of the intervention will be sufficiently high (see Table 1).

Study design:

Changes to the original study design were needed to accommodate the negative impact that the COVID-19 pandemic had in the partner FQHC system. We conducted a stepped-wedge design (SWD) trial with three sites, with data collection divided into 7 10-week intervals. Study sites remained in the intervention phase for multiple intervals to allow additional data to be collected. In addition to the 3 study sites, 2 additional sites from the same health system served as comparison sites, implementing ACEs screenings without the support of the implementation strategies. See Figure 1 for the SWD schedule.

Figure 1. Stepped-wedge schedule for the ACEs pilot study.

Study sites and patient eligibility:

The study statistician originally selected five clinics from a pool of 16 clinics providing family medicine, pediatric, or primary care for children ages 0 to 5 years old and across five regions to maximize variation (e.g., clinic characteristics such as resources and size). Clinics were located in urban, suburban, rural, and frontier communities. The study PI and FQHC champions invited the identified clinics via email to an informational video session to introduce the study and provided study informational materials to the clinic manager.

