Once the pilot study started, two randomly selected clinics were not able to participate - one clinic closed and one clinic lost their pediatrician leading ACEs screenings. Due to extremely high staff turnover at the clinics and among FQHC leadership, additional clinics selected were not able to participate in this research study. Thus, from the three clinics that finished the stepped wedge schedule, one was randomly selected and two clinics joined based on their capacity to participate in a research study at that time.

Eligible children were those aged 0-5, on public insurance, attending a wellness visit with the participating clinician.

Data sources:

Data for the primary outcomes, including reach of ACEs screenings and mental health referral rates, was obtained via the electronic medical record (EMR) at the partner health system. Additional data for secondary analyses was collected using REDCap among intervention patients only, including the PSC scores and ACEs screening results. See Figures 2 and 3 for the Consort tables.

Figure 2. CONSORT table for the study pilot study – Electronic Medical Records Data.

[figure not shown]

Figure 3. CONSORT table for sub-sample of data – REDCap system.

[figure not shown]

Table 1. Description of measures

Measure	Description/psychometrics	Source
ACEs Screening		
PEARLS¹ screening (ages 0-11)	Caregiver-reported tool (17-items) designed to identify exposure to childhood adversity and stress factors that may lead to toxic stress and negative health outcomes. Number of endorsed events are summed up (0-4+) to identify risk level for toxic stress and potential symptomatology. English/Spanish	Caregiver
ACEs associated health conditions²	State-sponsored list with 25 ACEs associated health conditions for children ages 0 – 5. ² Physical conditions include asthma, allergies, unexplained somatic symptoms such as headaches. Mental health related conditions (over 10) include aggression, depression, ADHD, and anxiety	EMR system

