Descriptive statistics will be used to describe the sample of children and clinics. The sample will be described using counts and percentages, and treatment groups will be compared using chi-squared tests. We will calculate risk differences with confidence limits for each of our three groups of interest- the study clinics during the control period, study clinics during the intervention period, and the control clinics. For subgroup analyses exploring differences by child demographics, we will calculate risk differences within those subgroups (age, gender, race, and ethnicity).

The reach variable (proportions screened) will be analyzed using binary regression (a generalized linear model, specifying a binomially-distributed dependent variable and identity link function). Modified Poisson regression with robust variance estimation¹⁴ will be used to analyze mental health referrals to estimate adjusted risk differences. Both models will compare the intervention and control arms as the primary independent variable of interest. Possible covariates will include child's sex, age category (<18 months, 18-60 months), child's race (white, black, other/unknown), child's ethnicity (Latino, not Latino, unknown/not reported), language of preference, and study site; covariates will be included in their adjustment changes the intervention regression coefficient by more than 15%.

Models comparing the intervention and comparison clinics will be adjusted for the child's race and for the study site. Missingness in demographic data will be handled by including an 'unknown or not reported' category. Survey data will be analyzed using aggregated intra-class correlations (ICC) to assess within-group agreement, whether clinic care teams shared perceptions of readiness for change during the preparation phase, and implementation climate and leadership. ICC is the variance proportion attributed to care teams.¹⁵ Higher scores in these measures reflect higher organizational support for the translation of a new clinical practice into practice.¹⁶ An agreement of 0.70 or higher reflects an organizational measure.¹⁷

References

1. National Pediatric Practice Community. PEARLS FAQs. Accessed August 14, 2019. <https://nppcaces.org/faqs/>
2. Aware A. ACES Screening Clinical Workflows. Accessed June 15, 2020. <https://www.acesaware.org/wp-content/uploads/2019/12/ACE-Clinical-Workflows-Algorithms-and-ACE-Associated-Health-Conditions.pdf>

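### The SAP was finalised after the trial ended and, without reason or date, replaces the protocol's clustering- and time-adjusted model with models that state neither adjustment

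*SAP*

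**What the plan says.** The SAP cover carries "Date: 7.20.2024". Its Study design section looks back on the trial: "We conducted a stepped-wedge design (SWD) trial with three sites, with data collection divided into 7 10-week intervals". Under Study sites and patient eligibility it writes that "from the three clinics that finished the stepped wedge schedule, one was randomly selected", the other two having joined because they had capacity. Under Data sources: "Data for the primary outcomes, including reach of ACEs screenings and mental health referral rates, was obtained via the electronic medical record".

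The hypotheses and the Statistical analysis section look forward. Reach gets a binomial regression with identity link, and referrals a modified Poisson regression with robust variance. Study site is listed among possible covariates, kept if adjustment moves the intervention coefficient by more than 15%. A separate sentence begins "Models comparing the intervention and comparison clinics will be adjusted for" and names child's race and study site. Only the subgroup questions (H1c, H2d) are called exploratory.

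Protocol section V.c (Data Analysis) plans a generalised linear mixed model (GLMM) for screening and referral, "controlling for clustering of patients within clinics and possible confounding by calendar time". It adds a sensitivity analysis with 10 imputed datasets. The protocol states "Version Date: 05/10/2024". In its study steps (V.1, step 4.11), for months 8 to 36, the study's "data analyst will lead data preparation and analysis and will meet weekly with the PI".

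The SAP attributes changes to the design, and to the protocol in general, to COVID-19. It does not mention the GLMM, and it neither lists nor dates any change of analysis.

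**The concern.** In a stepped-wedge trial each clinic's intervention periods come after its control periods. Any drift in screening or referral over calendar time is therefore mixed into the intervention contrast unless the model separates the two. Visits to the same clinic also tend to resemble one another, and ignoring this usually makes confidence limits too narrow. The protocol's model addresses both problems; the SAP's models, as written, state a remedy for neither.

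Such a change made before any outcome was seen, with a reason, is ordinary. Here the text was finalised once the data were in hand, and nothing records when or why the change was made. A reader of the results could not tell whether the conclusions on reach and referral depend on the choice of model, and the future tense would lead that reader to take the whole plan as prespecified.

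**Working it through.** No sample size, power or significance level is stated for H1 or H2, so there is no figure to reproduce. The check is date arithmetic followed by a comparison of the two texts.

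**1. Was the SAP finalised after the schedule ended?** By its own wording, yes: the trial was conducted, three clinics had finished the schedule, and the primary-outcome records had been obtained. This does not depend on the cover date.

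**2. Are the dates consistent with that?**
- Seven intervals × 10 weeks = 70 weeks = 490 days. Counting back 490 days from 20 July 2024 gives 18 March 2023, the latest start that allows completion by the SAP date.
- Protocol step 4.1 places a training set for May 2021 in month 1 or 2, so month 1 is April or May 2021.
- Planned trial end, month 30 (month 1 plus 29 months): September or October 2023.
- Planned end of analysis, month 36 (month 1 plus 35 months): March or April 2024, before 20 July 2024.
- From the protocol version of 10 May 2024 to the SAP date: 21 + 30 + 20 = 71 days. On this timetable the protocol version is also later than the planned trial end.

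These are planned months. Actual dates are not given and may have slipped.

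**3. What changed between the documents?**

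| Element | Protocol | SAP | Reason or date given |
|---|---|---|---|
| Model | GLMM for both outcomes | Binomial identity-link (reach); modified Poisson (referrals) | None |
| Clinic clustering | Controlled | Not stated; site only a possible covariate under the 15% rule, except in the comparison-clinic models | None |
| Calendar time | Controlled | No term stated | None |
| Missing data | Imputation as sensitivity analysis | Unknown category for demographics; imputation absent | None |
| Eligible children | Ages 0–5; no insurance or clinician filter | Ages 0–5, publicly insured, seen by the participating clinician | None |

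**4. What did not change?**
- H1a and H2a: protocol V.c contains the contrast with baseline on both screening and referral.
- H1b and H2b: protocol V.c contains the contrast with the comparison clinics on both outcomes, but only as an extra, non-randomised estimate.
- H2c (referral by risk level among screened children): no protocol counterpart.

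The contrasts and outcomes of the four main hypotheses thus have a source in the protocol. The SAP's models, covariate rule and eligibility filters do not, nor does H2c.

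**The case against.** The strongest reply is that the protocol is no clean benchmark. Its version is itself late, and section V.c explains in the past tense what the clinics had not done when the pilot started, so that part was written after the start. Agreement between two late documents would not make a result confirmatory. This stands, and it is why the remedy asks for dated sources for every choice.

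Second, the cover date may not date the choices. Both documents carry the July 2024 cover date although the protocol version is older, and the SAP retains older forward-looking text, such as a fidelity form still to be developed. Some analysis choices may be older than the cover suggests, and a protocol paper published in December 2021 (protocol V, dissemination plans) might date them. That is possible, but the SAP does not cite the paper and its content is not in these documents.

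Third, some differences are milder than they look. Public insurance fits the Medicaid-reimbursed policy and may be a clarification. The unknown category and the imputation analysis do not conflict; the point is only that the latter was dropped. If control periods had almost no screening, H1a may hardly depend on the model. These points reduce the weight of individual rows, but they do not explain the loss of clustering and calendar time from the stated models.

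Fourth, a mixed model with three study clinics and near-zero control reach may be unstable. That may be a good reason for the change, but the SAP does not give it.

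**Conclusion.** The point holds as one of undocumented order and of an unexplained change to the primary models. The SAP text was finalised after the schedule was complete and the primary data obtained. For H1a, H1b, H2a and H2b it drops, without reason or date, the stated control of calendar time and clinic clustering, apart from site adjustment in the comparison-clinic models. It also omits the imputation sensitivity analysis and adds two eligibility filters. This conclusion rests on the SAP's own wording; the month arithmetic is supporting and assumes the planned timetable.

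Three stronger readings are tempting and are not supported:
- **That choices were made because of the results.** The documents only fail to show the reverse, and the four main contrasts are in the protocol.
- **That naming race and site for the comparison-clinic models shows the 15% rule had already been run.** A fixed set for different models can be chosen in advance, and a change-in-estimate rule can itself be prespecified.
- **That the false-positive rate is raised by a known amount.** Neither document sets a significance level or shows how many analyses were tried, so no figure can be attached.

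The size of any effect on the risk differences is therefore unknown. Running the two analyses side by side would show it.

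**What to change.** - For each of H1a, H1b, H2a and H2b, report the protocol's analysis, with clinic clustering and calendar time controlled, next to the SAP's analysis. State any convergence failure or instability given three study clinics, and discuss any disagreement.
- Add to the SAP a short table giving, for each model, covariate and eligibility choice, the earliest dated source (for example the December 2021 published protocol, if it contains the choice), the reason for any change, and whether outcome data had been seen.
- Label every choice without a dated pre-data source, and H2c unless so sourced, as post hoc or exploratory.

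The cost is SAP wording and one additional model per hypothesis, four in all, on data already held. The mixed model may be unstable with three clinics, and some results may have to be called exploratory. If dated earlier records exist, citing them settles the question of order.

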b. Instrumentation

b.i. **Questionnaires/Survey Measures for the study (names and citations):**

- The Pediatric Symptoms Checklist is comprised of two measures based on age:
 - The Baby Pediatric Symptom Checklist (BPSC) is a 12-item screening measuring children's psychosocial function validated for children ages 0-18 months. Cronbach's alpha adequate for subscales (alpha=0.75 to 0.83).
 - The Preschool Pediatric Symptom Checklist (PPSC) is an 18-item screening for measuring children's psychosocial functioning validated for children ages 18-60 months. (alpha=0.92)

- The Feasibility of Intervention Measure (FIM) is a self-reported 4-item instrument to evaluate feasibility of implementation efforts. Good internal consistency (alpha =0.89). Test-retest reliability (r=0.88).
- The Acceptability of Intervention Measure (AIM) is a 4-item instrument to evaluate acceptability of implementation efforts. Good internal consistency (alpha =0.83). Test-retest reliability (r=0.83).
- Fidelity checklist form will be developed by principal investigator and [name].
- Implementation Leadership Scale is a 12-item scale with four subscales measuring proactive leadership, knowledgeable leadership, supportive leadership, and perseverant leadership. Reliability for the total scale is strong (alpha=0.98).
- Implementation Climate Scale is a 6-item scale measuring the strategic climate for the implementation of interventions.
- Readiness for Change is a 12-item scale measuring clinic staff and supervisors' perceptions of how prepared they are to start the ACEs screenings. This measure is only used at baseline for all clinics (Step 1 in the Stepped Wedge Design schedule).

b.ii. Qualitative instruments:

We will use a semi-structure interview protocols for Aim 2 in interviews with clinic personnel and with caregivers. We will allow participants to add in relevant areas of discussion. Each interview protocol has been uploaded to the IRB application.

c. Data Analysis

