Clinical screening tools	BPSC : 12-item screening measuring children's psychosocial functioning validated for children 0-18 months. Assesses irritability, inflexibility and difficulty with routines. ³ Designed for children 0-18 months; three subscales of four items each. Parents answer questions by selecting one of three responses: "not at all" = 0, "somewhat" = 1, "very much" = 2. Any summed score of 3+ on any of the three subscales indicates that a child is "at risk and needs further evaluation." Scores 0-2 indicates child "appears to meet expectations." Cronbach's alpha adequate for subscales (α =0.75 to 0.83). PPSC : 18-item screening for measurement of children's psychosocial functioning; validated for children ages 18-60 months. Assesses externalizing, internalizing, attention problems, and parenting challenges. ³ Parents select responses as: "not at all"=0; "somewhat"=1; "very much"=2. A score of 9+ indicates children is "at risk and needs further evaluation." α =0.92.	Caregiver
FIM⁴	Self-reported 4-item instrument to evaluate feasibility of implementation efforts. 4-pt Likert scale; average score of	Staff, manager

	4+ shows ACEs policy and implementation strategy perceived as feasible. Good internal consistency ($\alpha=0.89$). Test-retest reliability $r=0.88$.	provider
AIM⁴	Self-reported 4-item instrument to evaluate acceptability of ACEs policy and implementation efforts. 4-pt Likert scale; average score of 4+ shows acceptability. Good internal consistency ($\alpha=0.83$). Test-retest reliability $r=0.83$.	Staff manager provider
Fidelity	The implementation coach will use a checklist to observe the screening staff/providers at each clinic (once in week 5 of each 10-week trial period) to assess adherence to screening protocols and competence of performance. She will identify deviations/concerns and provide immediate feedback. We expect at least 67% fidelity (number of endorsed deviations / all items in the checklist) based on a previous study ⁵ The coach will also document adaptations and emerging challenges and report back to the PI and TIC workgroup. Form will be developed by PI & [name]. Observation checklists/ audits are effective strategies to improve fidelity of performance. ⁶	Implem coach

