Reach	Measured as a proportion = number of eligible visits in a 10-week period divided by the number of PEARLS and clinical (BPSC/PPSC) screenings. Expect between 80%-92% of eligible children will be screened as threshold; based on pediatric screening studies in primary care. ^{7,8}	EMR system
Mental health referrals	Number of mental health referrals (behavioral analysis, behavioral health, care coordinator, care management, child development/development center or social work) divided by the total # of eligible children in a 10-week trial period. expect 11.4% increased referral rate based on a similar study ⁹ and using current referral rate of 3.8% to inform this threshold [per i2itracks report	EMR system
Changes in BPSC/PPSC	Mean score differences from eligible child visits in each 10-week period. Compare those means in pre vs post implementation periods. No threshold as we will test a two-tail hypothesis for this measure given mixed evidence on the impact of screening policies on access to care and clinical outcomes. ^{10,11} Even if a positive effect is not found, this information is still valuable for implementation and leadership.	EMR system

Measures		
Implementation leadership (ILS)¹²	12-item scale with four subscales measuring proactive leadership, knowledgeable leadership, supportive leadership, and perseverant leadership. Reliability for the total scale is strong ($\alpha=0.98$). An average score of 4+ used as threshold; 5-point Likert scale (not at all-very great extent). Subscale score is based on the mean score for the items; total score is the mean of the subscale scores ¹² ;	Staff provider
Implementation climate¹³	6-item scale measuring the strategic climate for the implementation of interventions. The average interrater agreement: $r^*wg (J) = 0.76$ for the group referenced scale. Items are rated on a 5-item Likert scale (completely disagree-completely agree). Average score of 4+ as threshold ¹³	Staff provider
Covariates		
Child characteristic	Variables include sex, self-identified race and ethnicity, age, language of preference for health care receipt, born in the USA. Note: EMR system does not report data on caregivers of child patients	EMR system

Statistical analysis:

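### Two SAP Table 1 success rules are wrong as written: FIM and AIM can pass only at the scale maximum (or not at all), and the 67% fidelity target counts deviations

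*SAP*

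**What the plan says.** **FIM and AIM.** SAP Table 1 describes each as a four-item instrument on a four-point Likert scale with success at an average of 4 or more. The AIM row reads "4-pt Likert scale; average score of 4+ shows acceptability". The FIM row gives the same scale and ends "4+ shows ACEs policy and implementation strategy perceived as feasible". Hypothesis 3a depends on these rows, since it states that perceived feasibility, "acceptability, and usefulness of the intervention will be sufficiently high (see Table 1". The SAP gives no other definition of sufficiently high.

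**Other scales with the same cut.** In the same table, the implementation leadership row says "An average score of 4+ used as threshold; 5-point Likert scale", and the climate row says "Items are rated on a 5-item Likert scale (completely disagree-completely agree). Average score of 4+ as threshold".

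**Fidelity.** The coach observes staff with a checklist "to assess adherence to screening protocols and competence of performance". The target is then given as "We expect at least 67% fidelity (number of endorsed deviations / all items in the checklist".

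**Protocol.** Section V, Instrumentation, gives item counts and reliability for both scales but no response format or cut. For AIM it says "The Acceptability of Intervention Measure (AIM) is a 4-item instrument to evaluate acceptability of implementation efforts". It says only that the fidelity form will be developed. Section II names fidelity as an implementation outcome and includes it among the pilot's targets.

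**The concern.** A success threshold should separate good results from poor ones. The FIM/AIM mark sits at or above the top of the scale as described. Staff who were almost unanimously favourable would still be reported as not finding the strategy feasible or acceptable. The fidelity formula runs backwards, so the clinic that follows the procedure best gets the lowest score.

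For FIM and AIM this bears directly on whether Hypothesis 3a is reported as met. For fidelity it bears on a descriptive implementation outcome of the Protocol. The SAP describes the trial as already conducted, so a threshold quietly reinterpreted at reporting could be challenged as chosen after the results were known.

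**Working it through.** The plan derives no figure here that could be reproduced. The check is whether each rule does what its row says it does.

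**1. FIM and AIM**

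Inputs from SAP Table 1: 4 items, 4 response points, cut at a mean of 4. Coding and unit of averaging are not stated.

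- *Coded 1 to 4.* The maximum mean is (4+4+4+4)/4 = 4. Of the 4^4 = 256 response patterns for one respondent, only one reaches 4. One answer of 3 gives (4+4+4+3)/4 = 3.75.
- *Pooled over n respondents, coded 1 to 4, a single answer of 3 and all others 4.* Mean = 4 − 1/(4n). For assumed n of 5, 10 and 20 this is 3.95, 3.975 and 3.9875. All are below 4 before rounding, and no rounding rule is given.
- *Coded 0 to 3.* The maximum mean is 3, so the mark cannot be met.

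Position of the cut within the scale, (cut − minimum)/(maximum − minimum):

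| Scale | Position of 4 | Patterns of four items with mean ≥ 4 |
|---|---|---|
| 1 to 4 | 3/3 = 100% | 1 of 256 |
| 1 to 5 | 3/4 = 75% | 70 of 625 |
| 0 to 4 | 4/4 = 100% | 1 of 625 |

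The 70 comes from allowing a total shortfall of 0 to 4 points from 20: 1 + 4 + 10 + 20 + 35 = 70. A cut of 4 therefore behaves like an ordinary threshold on a five-point scale coded 1 to 5. The leadership and climate rows also have five response points, which suggests that the slip lies in the FIM/AIM scale description. The last line shows that coding has to be stated even then.

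The FIM row is split by a page break in the available text. The AIM row is unbroken and says the same, so this is not a fault of text extraction.

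**2. Fidelity**

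Inputs from SAP Table 1: target at least 67%; score = deviations / all items. Assume each item is scored either adherent or deviant. Then the score as written = 1 − adherence.

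| Adherence | Score as written | At least 67%? |
|---|---|---|
| 100% | 0% | fails |
| 80% | 20% | fails |
| 67% | 33% | fails |
| 33% | 67% | passes |
| 0% | 100% | passes |

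The written rule needs 1 − adherence ≥ 0.67, that is adherence ≤ 0.33. The evident intention needs adherence ≥ 0.67. No clinic can meet both. On an assumed 10-item checklist, the written rule passes with 7 or more deviations and the intended one with 3 or fewer.

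**3. Whether another section settles it**

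- Protocol, Instrumentation: no response format for FIM or AIM, and no fidelity formula.
- SAP, Statistical analysis: survey data are to be examined for within-group agreement, naming readiness, climate and leadership. It gives no unit of averaging for FIM or AIM and no fidelity calculation.

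Neither rule is corrected elsewhere.

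**The case against.** The strongest reply is that these are drafting slips that any analyst would see through. For fidelity much of this stands. The row says it measures adherence, nobody is likely to report a faultless clinic as 0%, the 67% is worded as an expectation, and no SAP hypothesis or analysis uses it. The 1 − adherence arithmetic also depends on yes/no items. The form was still to be developed and also covers competence, so its scoring could be more complex.

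For FIM and AIM the reply is weaker. It is true that the SAP specifies no formal test on them, so the cut is a descriptive benchmark. But Hypothesis 3a has no other criterion, and good sense cannot tell the reader whether the scale length or the cut is wrong. The two errors need different corrections.

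A reader might also go further than the documents allow:

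- *That the FIM/AIM mark is impossible.* This holds only under 0 to 3 coding. Coded 1 to 4 it can be reached, at the ceiling.
- *That the scale was certainly five-point.* The neighbouring rows suggest it, but neither document states it.
- *That three of the Protocol's four pilot targets (feasibility, acceptability, fidelity) have faulty rules and reach has a sound one.* The Table 1 reach row is itself inverted, with eligible visits over screenings. Protocol Section II gives that ratio the right way up. A count of faulty targets would therefore mislead.
- *That usefulness should be struck from Hypothesis 3a.* It has no row or threshold in Table 1, and the staff survey content listed in the Protocol's study steps does not name it. Interviews with staff and caregivers may cover it, and the interview guides are not in these documents. Deleting it now would itself be a post hoc change.

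**Conclusion.** Both rules are wrong as written, and neither is corrected elsewhere. The FIM/AIM mark is 100% of the range if coded 1 to 4 and out of reach if coded 0 to 3. The same cut is 75% of the range on a 1 to 5 scale. This is the weightier half, because it is the decision criterion for two elements of Hypothesis 3a. The fidelity rule is a plain inversion: adherence of 33% or less passes and anything higher fails, provided items are scored adherent or deviant. Its intended direction is evident, so that half is a wording correction to a Protocol implementation outcome.

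Neither rule affects the primary analyses of reach and mental health referrals. The respondent numbers and checklist length in the working are assumptions for illustration. The conclusions do not depend on them.

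**What to change.** 1. **FIM and AIM rows.** State the response format and numerical coding actually fielded, and whether the average is per respondent, per clinic or pooled.
   - If the scale was five-point coded 1 to 5, correct the description and keep 4+.
   - If it was four-point, say that the written mark is the ceiling (or cannot be reached, under 0 to 3 coding) and report means and response distributions. Label any lower mark as post hoc, with its date and whether scores had been seen when it was set. The same applies to a five-point scale coded 0 to 4.
2. **Fidelity row.** Define the score as items adhered to / all checklist items, which equals 1 − (deviations / items) when items are scored yes/no, and keep at least 67%. State how any competence items are scored.
3. **Hypothesis 3a.** At most, add a note that usefulness has no measure or threshold in Table 1, and report it as such.

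The cost is a few words in three table rows, an optional note, and recalculation from survey and checklist data already planned. No new data are needed.
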